## 7 STUDY ENDPOINTS

### 7.1 Primary Endpoint

Absolute change in ppFEV1 from baseline at Week 4

### 7.2 Secondary Endpoints

#### 7.2.1 Key Secondary Endpoints

- Absolute change in sweat chloride (SwCl) from baseline at Week 4
- Absolute change in CFQ-R respiratory domain score from baseline at Week 4

#### 7.2.2 Other Secondary Endpoints

- Safety and tolerability assessments based on adverse events (AEs), clinical laboratory values, ECGs, vital signs, and pulse oximetry
- PK parameters of VX-445, TEZ, M1-TEZ, and IVA

## 8 STUDY POPULATION

Eligibility will be reviewed and documented by an appropriately qualified member of the investigator's team before subjects receive study drug on Day -28.

Subjects who meet all of the inclusion criteria and none of the exclusion criteria will be eligible.

### 8.1 Inclusion Criteria

1. Subject (or his or her legally appointed and authorized representative) will sign and date an informed consent form (ICF), and, when appropriate, an assent form.
2. Willing and able to comply with scheduled visits, treatment plan, study restrictions, laboratory tests, contraceptive guidelines, and other study procedures.

3. Age 12 years or older, on the date of informed consent.
4. Confirmed diagnosis of CF as determined by the investigator.
5. Subject has the F/F genotype. Note: If the screening *CFTR* genotype result is not received before Day -28, a previous *CFTR* genotype laboratory report may be used to establish eligibility. Subjects who have been enrolled and whose screening genotype is not confirmed to be F/F must be discontinued from the study (Section 9.9).
6. Forced expiratory volume in 1 second (FEV1) value  $\geq 40\%$  and  $\leq 90\%$  of predicted mean for age, sex, and height (equations of the Global Lung Function Initiative [GLI]) at the Screening Visit. Spirometry measurements must meet American Thoracic Society/European Respiratory Society criteria for acceptability and repeatability.
7. Stable CF disease as judged by the investigator.
8. Willing to remain on a stable CF treatment regimen (as defined in Section 9.5) through completion of study participation.

## 8.2 Exclusion Criteria

1. History of any illness or any clinical condition that, in the opinion of the investigator, might confound the results of the study or pose an additional risk in administering study drug(s) to the subject. This includes, but is not limited to, the following:
  - Clinically significant cirrhosis with or without portal hypertension.
  - Solid organ or hematological transplantation.
  - Alcohol or drug abuse in the past year, including, but not limited to, cannabis, cocaine, and opiates, as deemed by the investigator.
  - Cancer, except for squamous cell skin cancer, basal cell skin cancer, and Stage 0 cervical carcinoma in situ (all 3 with no recurrence for the last 5 years).
2. Any of the following abnormal laboratory values at screening:
  - Hemoglobin  $< 10$  g/dL
  - Total bilirubin  $\geq 2 \times$  ULN
  - Aspartate transaminase (AST), alanine transaminase (ALT), gamma-glutamyl transferase (GGT), or alkaline phosphatase (ALP)  $\geq 3 \times$  ULN
  - Abnormal renal function defined as glomerular filtration rate  $\leq 50$  mL/min/1.73 m^2 (calculated by the Modification of Diet in Renal Disease Study Equation) for subjects  $\geq 18$  years of age and  $\leq 45$  mL/min/1.73 m^2 (calculated by the Counahan-Barratt equation) for subjects aged 12 to 17 years (inclusive)
3. An acute upper or lower respiratory infection, pulmonary exacerbation(s) (PEX), or changes in therapy (including antibiotics) for sinopulmonary disease within 28 days before the first dose of TEZ/IVA in the Run-in Period (Day -28).
4. Lung infection with organisms associated with a more rapid decline in pulmonary status (including, but not limited to, *Burkholderia cenocepacia*, *Burkholderia dolosa*, and *Mycobacterium abscessus*). For subjects who have had a history of a positive culture, the

investigator will apply the following criteria to establish whether the subject is free of infection with such organisms:

- The subject has not had a respiratory tract culture positive for these organisms within the 12 months before the date of informed consent.
  - The subject has had at least 2 respiratory tract cultures negative for such organisms within the 12 months before the date of informed consent, with the first and last of these separated by at least 3 months, and the most recent one within the 6 months before the date of informed consent.
5. An acute illness not related to CF (e.g., gastroenteritis) within 14 days before the first dose of TEZ/IVA in the Run-in Period (Day -28).
  6. Ongoing or prior participation in a study of an investigational treatment other than a Vertex CFTR modulator within 28 days or 5 terminal half-lives (whichever is longer) before screening. The duration of the elapsed time may be longer if required by local regulations.
  7. Use of prohibited medications as defined in [Table 9-2](#), within the specified window before the first dose of TEZ/IVA in the Run-in Period (Day -28).
  8. Pregnant or nursing females. Females of childbearing potential must have a negative pregnancy test at Screening/Day -56 (serum test) and TEZ/IVA Run-in Period/Day -28 (urine test).
  9. The subject or a close relative of the subject is the investigator or a subinvestigator, research assistant, pharmacist, study coordinator, or other staff directly involved with the conduct of the study at that site. However, an adult (aged 18 years or older) who is a relative of a study staff member may be enrolled in the study provided that
    - the adult lives independently of and does not reside with the study staff member, and
    - the adult participates in the study at a site other than the site at which the family member is employed.

[figure not shown]
## **9 STUDY IMPLEMENTATION**

### **9.1 Study Design**

This is a Phase 3, randomized, double-blind, active-controlled, parallel-group, multicenter study. A schematic of the study design is shown in [Figure 9-1](#).

**Figure 9-1 Schematic of the Study Design**

IVA: ivacaftor; N: number of subjects; TC: triple combination; TEZ: tezacaftor

Note: The Safety Follow-up Visit is not required for subjects who complete the Week 4 Visit and have enrolled in an open-label study within 28 days after the last dose of study drug (Section 9.1.4).

Study drug is defined in Section 10.

All subjects entering the TEZ/IVA Run-in Period will receive TEZ 100 mg once daily (qd)/IVA 150 mg every 12 hours (q12h). Following completion of the TEZ/IVA Run-in Period, approximately 100 subjects will be randomized (1:1) to the TC arm or TEZ/IVA arm for the Treatment Period. The planned dosages for the Treatment Period are shown in Table 9-1. Randomization will be stratified; details are provided in Section 9.2.

**Table 9-1 Treatment Period Arms and Dosages**

Treatment Arm	VX-445 Dosage	TEZ Dosage	IVA Dosage
TC	200 mg qd	100 mg qd	150 mg q12h
TEZ/IVA	0 mg	100 mg qd	150 mg q12h

IVA: ivacaftor; q12h: every 12 hours; qd: once daily; TC: triple combination; TEZ: tezacaftor

Note: Study drug administration is described in Section 9.6.

Study visits and assessments to be conducted are shown in Table 3-1 and Table 3-2. All visits will occur within the windows specified.

**9.1.1 Screening**

The Screening Period (Day -56 through Day -29) will occur within 28 days before the first dose of study drug in the Run-in Period.

Screening assessments will be used to confirm that subjects meet the eligibility criteria. The investigator (or an appropriate authorized designee) will obtain informed consent and assent, if applicable, from each subject before any study procedure takes place.

### 9.1.1.1 Repetition of Screening Assessment(s)

Screening assessments may be repeated once to establish study eligibility. If repeat values of the individual assessment(s) are within the eligibility criteria and completed within the screening window, then the subject is eligible for the study.

### 9.1.1.2 Rescreening

Subjects may be rescreened once. If a subject is rescreened, all screening assessments will be repeated, except for:

- *CFTR* genotyping
- Follicle-stimulating hormone (FSH) level (if serum FSH level was in the postmenopausal range as determined by the laboratory performing the test during prior screening)
- G6PD activity test
- Ophthalmologic examination (if performed within 3 months of the date of informed consent, for subjects <18 years of age)

If a subject is rescreened, a new screening window will begin when the first rescreening assessment has been initiated.

### 9.1.1.3 Extension of Screening Period Window

A subject may have the Screening Period window extended by 2 weeks for the following reasons:

- Repetition of the Screening Period assessments (Section 9.1.1.1)
- Unexpected operational or logistic delays, or to meet the eligibility criteria
- Scheduling of ophthalmologic examination (for subjects <18 years of age on the date of informed consent, [Section 11.7.6](#))

### 9.1.2 Tezacaftor/Ivacaftor Run-in Period

The TEZ/IVA Run-in Period has a 4-week duration and is designed to establish a reliable on-treatment (TEZ/IVA) baseline for the Treatment Period. The first dose of open-label TEZ/IVA will be administered at the Day -28 Visit. The last dose of open-label TEZ/IVA will be administered in the evening on Day -1 (1 day before the Day 1 Visit).

On Day -14, spirometry and SwCl will be assessed. The Day -14 spirometry assessment will be used for stratification of randomization ([Section 9.2](#)).

Subjects who prematurely discontinue study drug treatment during the Run-in Period will not be randomized or participate in the Treatment Period ([Section 9.1.5.1](#)).

### 9.1.3 Treatment Period

The Treatment Period will be randomized, double-blind, and active-controlled. It will last approximately 4 weeks (Day 1 to Week 4). Study drug administration details are provided in [Section 9.6](#).

Randomization will occur before the first dose of study drug during the Treatment Period and may occur on either Day -1 or Day 1. Randomization and stratification details are provided in [Section 9.2](#).

To enter the Treatment Period, subjects must have stable CF disease (as judged by the investigator) and have remained on a stable CF treatment regimen during the TEZ/IVA Run-in Period. Female subjects of childbearing potential also must have a negative pregnancy test at Day 1 before receiving randomized study drug. If these conditions are not met (for example, if the subject has an acute upper or lower respiratory infection, PEx, or changes in therapy [including antibiotics] for sinopulmonary disease within 28 days before the Day 1 Visit [first dose of study drug in the Treatment Period]), the subject is considered a run-in failure and cannot enter the Treatment Period or rescreen.

Subjects who prematurely discontinue study drug treatment during the Treatment Period will remain in the study from the time of discontinuation of study drug treatment through the last scheduled study visit and complete the assessments for all study visits, as described in [Section 9.1.5.2](#).

#### **9.1.4 Follow-up**

The Safety Follow-up Visit will occur approximately 28 days after the last dose of study drug for subjects who complete study drug dosing and for subjects who prematurely discontinue study drug dosing, as described in [Section 9.1.5](#).

An open-label study will be available for subjects who complete the Week 4 Visit and are eligible. The Safety Follow-up Visit is not required for subjects who complete the Week 4 Visit and enroll in an open-label study within 28 days after the last dose of study drug.

#### **9.1.5 Early Termination of Treatment**

If a subject prematurely discontinues study drug treatment, an Early Termination of Treatment (ETT) Visit should be scheduled as soon as possible after the decision to discontinue treatment. Subjects who prematurely discontinue treatment will also be required to complete the Safety Follow-up Visit, approximately 28 days after their last dose of study drug. The assessments performed at the Safety Follow-up Visit are listed in [Table 3-2](#).

If the ETT Visit occurs 3 weeks or later following the last dose of study drug, then the ETT Visit will replace the Safety Follow-up Visit, and a separate Safety Follow-up Visit will not be required.

If a subject withdraws from the study and also withdraws consent or assent, no further assessments will be performed. Vertex may retain and continue to use any data and samples collected before such withdrawal of consent or assent.

##### **9.1.5.1 Discontinuation During the Run-in Period**

Subjects who prematurely discontinue study drug treatment during the Run-in Period will not be randomized or participate in the Treatment Period. These subjects will complete an ETT Visit and Safety Follow-up Visit (as applicable; see [Section 9.1.5](#)). The Safety Follow-up Visit will be their last visit in the study.

### **9.1.5.2 Discontinuation During the Treatment Period**

Subjects who prematurely discontinue study drug treatment during the Treatment Period will continue to complete all scheduled study visits for assessments following completion of the ETT Visit, as detailed in [Table 3-2](#). Data regarding concomitant antibiotic therapy for sinopulmonary signs/symptoms will also continue to be collected for these subjects. These subjects will complete an ETT Visit and Safety Follow-up Visit (as applicable; see [Section 9.1.5](#)). The Safety Follow-up Visit will be their last visit in the study.

### **9.1.6 Lost to Follow-up**

A subject will be considered lost to follow-up if both of the following occur:

- The subject misses 2 consecutive study visits (telephone contact and/or clinic visit) and is subsequently unable to be contacted by telephone (3 documented attempts by telephone within 2 weeks following the second missed visit)
- The subject does not respond within 2 weeks to a registered letter sent after the 3 attempted telephone contacts.

### **9.1.7 Completion of Study Participation**

Completion of study participation for each individual subject is defined as one of the following:

- For subjects who complete the Treatment Period and enter an open-label study within 28 days of the Week 4 Visit: the Week 4 Visit
- For subjects who complete the Treatment Period and do not enter an open-label study within 28 days of the Week 4 Visit: the Safety Follow-up Visit
- For subjects who prematurely discontinue study drug treatment during the Treatment Period but do not withdraw consent (and assent, as applicable): The ETT or Safety Follow-up Visit (if required)
- For subjects who prematurely discontinue study drug treatment during the TEZ/IVA Run-in Period but do not withdraw consent (and assent, as applicable): the ETT or Safety Follow-up Visit (if required)
- For subjects who withdraw consent or assent: date of withdrawal of consent or assent, whichever is earlier ([Section 9.9](#))

If subjects are lost to follow-up ([Section 9.1.6](#)), the date of completion of study participation will be defined as the date of the last contact.

The end of study is defined in [Section 13.2.8](#).

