**Table 3-2 VX17-445-103: TEZ/IVA Run-in Period, Treatment Period, and Safety Follow-up Visit**

Event/Assessment a	TEZ/IVA Run-in Period (4 Weeks)		Treatment Period (4 Weeks)			ETT Visit b	Safety Follow-up Visit 28 (± 7) Days After the Last Dose of Study Drug (If Applicable) c
	Day -28 ± 1 Day	Day -14 (Day -15 to Day -3)	Day 1 d	Day 15 ± 3 Days	Week 4 ± 5 Days		
Run-in TEZ/IVA dosing q	Day -28 to evening on Day -1						
Run-in TEZ/IVA drug count	X	X	X				
Randomization r			X				
Randomized study drug dosing s			Day 1 through evening before the Week 4 Visit				
Randomized study drug count			X	X	X	X	
Medications review u	Continuous from signing of ICF through completion of study participation						
Treatments and procedures review u	Continuous from signing of ICF through completion of study participation						
AEs and SAEs u, v	Continuous from signing of ICF through completion of study participation						

AE: adverse event; CF: cystic fibrosis; CFQ-R: CF Questionnaire-Revised; ETT: Early Termination of Treatment; GPS: Global Patient Safety; ICF: informed consent form; IV: intravenous; IVA: ivacaftor; PD: pharmacodynamic; ██████████; PK: pharmacokinetic; ██████████; SAE: serious adverse event; TEZ: tezacaftor; ██████████

q For the Run-in Period, TEZ/IVA should be administered as outlined in Section 9.6.1. On days of scheduled visits, refer to Section 9.6.1 for the timing of dosing relative to the assessments. The final dose during the Run-in Period will be administered on Day -1, the evening before the Day 1 Visit.

r Randomization may occur on either Day -1 or Day 1, after conditions for entry into the Treatment Period (Section 9.1.3) have been satisfied. Randomization must occur before the first dose of study drug in the Treatment Period.

s For the Treatment Period, the randomized study drug regimen should be administered as outlined in Section 9.6.1. On days of scheduled visits, refer to Section 9.6.1 for the timing of dosing relative to the assessments. The final dose of study drug in the Treatment Period will be administered the evening before the Week 4 Visit.

Completion of study participation is defined in Section 9.1.7.

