## **12.3 Statistical Analysis**

### **12.3.1 General Considerations**

**Continuous variables** will be summarized using the following descriptive summary statistics: the number of subjects (n), mean, SD, median, minimum value (min), and maximum value (max). The precision of the measurement for each continuous variable will be specified in the SAP. Unless otherwise specified, min and max values will be reported with the same precision as the units of the raw data. The mean, median, and SD will be reported to 1 additional decimal place. Any values that require a transformation to standard units (metric or SI) will be converted with the appropriate precision.

**Categorical variables** will be summarized using counts and percentages. Percentages will be presented to 1 decimal place.

The **baseline value**, unless otherwise specified, will be defined as the most recent non-missing measurement (scheduled or unscheduled) collected before the first dose of study drug in the Treatment Period (i.e., the Day 1 Visit). For ECG, baseline will be defined as the most recent pretreatment measurement (or the average of triplicate measurements, if the most recent pretreatment measurement is obtained in triplicate) before the first dose of study drug in the Treatment Period (i.e., the Day 1 Visit).

**Absolute change** from baseline will be calculated as post-baseline value – baseline value.

The **Treatment-emergent (TE) Period for the Run-in Period** will be from the first dose date of study drug in the Run-in Period to (1) the first dose date of study drug in the Treatment Period for subjects who complete the Run-in Period and continue to the Treatment Period, or (2) 28 days after the last dose date of study drug in the Run-in Period or to the completion of study participation date, whichever occurs first, for subjects who do not continue to the Treatment Period (e.g., subjects who do not meet the conditions to enter the Treatment Period).

The **TE Period for the Treatment Period** will include the time from the first dose date of study drug in the Treatment Period (TC or placebo + TEZ/IVA) to 28 days after the last dose of the study drug or to the completion of study participation date (as defined in [Section 9.1.7](#)), whichever occurs first.

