### **13.1.1.3 Documentation of Adverse Events**

All AEs will be collected from the time the ICF is signed until the subject completes study participation, as defined in [Section 9.1.7](#).

All subjects will be queried, using nonleading questions, about the occurrence of AEs at each study visit. When possible, a constellation of signs and/or symptoms will be identified as 1 overall event or diagnosis. All AEs for enrolled subjects will be recorded in the CRF and source document. AEs for subjects who are screened but not subsequently enrolled in the study will be recorded only in the subject's source documents. The following data will be documented for each AE:

- Description of the event
- Classification of "serious" or "nonserious"
- Date of first occurrence and date of resolution (if applicable)
- Severity
- Causal relationship to study drug(s)
- Action taken
- Outcome
- Concomitant medication or other treatment given

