### **13.1.2.2 Documentation of Serious Adverse Events**

All SAEs that occur after obtaining informed consent through completion of study participation, regardless of causality, will be reported by the investigator to Vertex GPS. In addition, all SAEs that occur after completion of study participation and are considered related to study drug(s) will be reported to Vertex GPS **within 24 hours**.

SAEs will be recorded on the Vertex Organized Safety Information Collection Form (hereafter referred to as the “SAE Form”) using a recognized medical term or diagnosis that accurately reflects the event. SAEs will be assessed by the investigator for relationship to the investigational study drug(s) and possible etiologies. On the SAE Form, relationship to study drug(s) will be assessed only as related (includes possibly related) or not related (includes unlikely related), and severity assessment will not be required. For the purposes of study analysis, if the event has not resolved at the end of the study reporting period, it will be documented as ongoing. For purposes of regulatory safety monitoring, the investigator is required to follow the event to resolution and report to Vertex the outcome of the event using the SAE Form.

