9 STATISTICAL ANALYSIS

9.1 General Considerations

The Schedule of Assessments is provided in Section 3 of CSP. The precision standards for reporting safety and efficacy variables are provided in an internal Biometrics document that specifies the programming rules including the precision for derived variables.

Continuous variables will be summarized using the following descriptive summary statistics: the number of subjects (n), mean, SD, median, minimum value (min), and maximum value (max).

Categorical variables will be summarized using counts and percentages. Percentages will be presented to 1 decimal place.

Baseline value, unless otherwise specified, is defined as the most recent non-missing measurement (scheduled or unscheduled) collected before the first dose of study drug in the Treatment Period.

Absolute change from baseline will be calculated as post-baseline value – baseline value.

Relative change from baseline will be calculated as (post-baseline value – baseline value)/baseline value.

The **Treatment-emergent (TE) Period for the Run-in Period** will be from the first dose of study drug in the Run-in Period to

- 1) for subjects who complete the run-in period and continue to the Treatment Period, the first dose of study drug in the Treatment Period, or

- 2) for subjects who do not continue to the Treatment Period, either 28 days after the last dose date of study drug in the Run-in Period, or to the completion of study participation date, whichever occurs first.

The **TE Period for the Treatment Period** will include the time from the first dose date of study drug in the Treatment Period (TC or placebo + TEZ/IVA) to 28 days after the last dose of the study drug or to the completion of study participation date, whichever occurs first.

Unscheduled visits: Unscheduled visit measurements will be included in analysis as follows:

- 1) In scheduled visit windows per specified visit windowing rules
- 2) In the derivation of baseline and last on-treatment measurements
- 3) In the derivation of maximum and minimum values during TE period, and maximum and minimum change from baseline values during TE period for safety analyses
- 4) In individual subject data listings as appropriate

Visit windowing rules: The analysis visit windows for protocol-defined visits are provided in [Appendix A](#).

Incomplete/missing data will not be imputed, unless specified otherwise.

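### Subjects who enter an open-label study after the Week 4 Visit but within 28 days of it are dated complete at Week 4, so adverse event collection and the treatment-emergent period end one day after the last dose

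*Protocol*

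**What the plan says.** Four sets of provisions bear on this point.

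- **Completion.** Protocol 9.1.7 gives, for open-label entrants: "For subjects who complete the Treatment Period and enter an open-label study within 28 days of the Week 4 Visit: the Week 4 Visit". The date does not depend on the day of entry within those 28 days.
- **Collection.** Protocol 13.1.1.3 states: "All AEs will be collected from the time the ICF is signed until the subject completes study participation", and refers to 9.1.7 for the definition. The AE and SAE row of Table 3-2 reads "Continuous from signing of ICF through completion of study participation". After completion, 13.1.2.2 keeps one class of event reportable: "all SAEs that occur after completion of study participation and are considered related to study drug(s) will be reported to Vertex GPS".
- **TE Period.** It runs from the first Treatment Period dose "to 28 days after the last dose of the study drug or to the completion of study participation date, whichever occurs first" (SAP 9.1; protocol 12.3.1 has the same rule). Safety summaries use TE data. Post-treatment AEs go to individual listings (protocol 12.3.4.1, SAP 9.4.1).
- **Safety Follow-up waiver.** Protocol 9.1.4 waives the visit for subjects who complete Week 4 and "enroll in an open-label study within 28 days after the last dose of study drug". The synopsis, Table 3-2, the Figure 9-1 note and the SAP Figure 7-1 note also count from the last dose.

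Entry on a day other than the Week 4 Visit is foreseen: Table 3-2 footnote n and protocol 11.3.1 give separate PK sampling instructions for subjects who do not enter that day.

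**The concern.** Safety is a secondary objective, and the tables of treatment-emergent AEs (TEAEs) are its main summary. Both documents set 28 days after the last dose as the outer limit for a TEAE. For a delayed entrant the completion date overrides that limit and cuts off-drug follow-up in the tables to one day, even though the subject has not yet started the next study.

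A non-serious AE, or an SAE judged unrelated, that begins in this interval is outside the stated collection window. If it is recorded with a full onset date, it is excluded from the TEAE tables. No visit is scheduled in the interval when Safety Follow-up is waived, and AEs are elicited at visits: "All subjects will be queried, using nonleading questions, about the occurrence of AEs at each study visit".

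The two 28-day clocks add a small contradiction about who still needs a Safety Follow-up Visit.

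**Working it through.** The check is calendar arithmetic on the plan's own rules.

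**Inputs**
- Week 4 Visit W = Day 29 (target day, SAP Appendix A).
- Last dose L = W − 1 = Day 28 (evening before the Week 4 Visit, Table 3-2 footnote s).
- Completion for entry within 28 days of Week 4 = W (protocol 9.1.7).
- TE end = the earlier of L + 28 and completion (protocol 12.3.1, SAP 9.1).
- Safety Follow-up window = L + 28 ± 7 days (Table 3-2).

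**Plan's reference horizon.** L + 28 = 28 + 28 = Day 56. A subject who does not roll over completes at Safety Follow-up, between Day 28 + 21 = 49 and Day 28 + 35 = 63. TE end is then min(56, 49 to 63) = Day 49 to 56, which is 21 to 28 days after the last dose.

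**Delayed entrant.** TE end = min(56, 29) = Day 29, one day after the last dose. AE collection also ends on Day 29. Full days between the Week 4 Visit and entry = entry day − W − 1:

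| Entry day | Full days in the gap | TE end now | TE end if closed at entry or L + 28 |
|---|---|---|---|
| 29 (same day) | 0 | 29 | 29 |
| 36 | 36 − 29 − 1 = 6 | 29 | 36 |
| 43 | 43 − 29 − 1 = 13 | 29 | 43 |
| 56 | 56 − 29 − 1 = 26 | 29 | 56 |
| 57 | 57 − 29 − 1 = 27 | 29 | 56 |

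Every gap day is on or before Day 56. It is therefore inside last dose plus 28 days but outside both windows. The gap depends only on entry day minus W, so it is the same at either end of the Week 4 visit window (Day 24 or 34).

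**The two clocks.** The 9.1.4 limit is L + 28 = Day 56. The 9.1.7 limit is W + 28 = 29 + 28 = Day 57. They differ by W − L = 1 day. A subject who enters on Day 57 is complete at Week 4 under 9.1.7, but misses the waiver in 9.1.4 and still owes a Safety Follow-up Visit.

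**SAE provisions side by side.** Protocol 13.1.2.2 requires all SAEs up to completion and only related ones afterwards. Protocol 13.1.2.3 asks for notification within 24 hours whatever the suspected cause, and gives no time window. Read together, 13.1.2.2 appears to supply the window, but the text does not say so.

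**The case against.** The strongest reply is that this is a labelling rule for off-drug events in descriptive tables, and much of that stands.

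- At Week 4 nobody knows whether a subject will enter later. Those who do not are followed to Safety Follow-up, so sites may well keep recording.
- AEs already ongoing are followed to a final outcome (protocol 13.1.1.7). The gap concerns new or worsened events only.
- The separate SAE and death listings carry a flag for TEAE status (SAP 9.4.1), so serious gap events remain identifiable.
- Protocol 13.1.2.3 can be read as asking for all SAEs.
- On the protocol's dosing rule, the clock conflict is one day.

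None of this changes the classification: a recorded gap AE with a full onset date is still post-treatment.

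A reader might infer more than the documents support:

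- **That data are lost.** Not shown. Continued recording is plausible, and the open-label study's AE collection is not among the documents.
- **That the arms are compared unfairly.** Not shown. The rule is the same in both arms and safety is not tested.
- **That the clocks can differ by several days.** SAP 9.2.6 mentions interruptions running to the end of participation, but only for the compliance formula. It does not say that such a subject completes the Treatment Period; the subject may instead fall under the premature-discontinuation rule in 9.1.7.
- **That incomplete onset dates are part of this problem.** The imputation rules in SAP Appendix E can move an event across any TE boundary, including for subjects who never roll over.

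**Conclusion.** The point holds as a minor one that is cheap to correct. For Treatment Period completers who enter an open-label study after the Week 4 Visit but within 28 days of it, the stated AE window and the TE Period close one day after the last dose. In the reference case, up to 26 full days (entry on Day 56) or 27 (entry on Day 57) lie within the plan's own 28-day limit but outside both windows. Fully dated new or worsened AEs in those days appear in listings, not in the TEAE tables.

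The figures assume Week 4 on its target day and a last dose the evening before. The number of delayed entrants is not given, so the effect on any table cannot be sized. The one-day mismatch between 9.1.4 and 9.1.7 is a direct textual conflict, though a small one.

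**What to change.** 1. **TE Period** (protocol 12.3.1, SAP 9.1). For these subjects, end the Treatment Period TE Period at open-label entry or at last dose plus 28 days, whichever is first. Define entry as one dated event, for example open-label consent or first open-label dose.
2. **Collection** (protocol 13.1.1.3, 13.1.2.2, Tables 3-1 and 3-2 including footnote v, and 11.7.5). Run AE and SAE collection to that same event, with one AE query at that contact. Over the same span, collect the medications and treatments given for those AEs (9.5, Table 3-2), because 13.1.1.3 requires them for each AE. State explicitly how 13.1.2.2 and 13.1.2.3 fit together. Leave the 9.1.7 date in place for the medication restrictions and the stable-regimen requirement, which are tied to it.
3. **Clocks and terms.** Reconcile the 28-day anchor and the verbs *enroll* and *enter* across the synopsis, Table 3-2, the Figure 9-1 note, 9.1.4, 9.1.7 and the SAP Figure 7-1 note.

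The cost is wording in these places and one AE query at entry, with no new clinic visit. Medication classes follow the TE Period (protocol 12.3.2.3, SAP 9.2.4), so some gap medications would become concomitant. TE follow-up would still differ between subjects: one day after the last dose with same-day entry, against 21 to 28 days without rollover. The change does not make follow-up equal. It stops the tables from closing before the subject has entered the next study or reached the 28-day limit.
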